5.0 Study Procedures

5.1 Procedures for FGDs with couples: We will conduct two FGDs with 3-4 couples (6-8 individuals) each. We will recruit couples using procedures from our prior studies with couples in South Africa and Malawi. A team of recruiters will approach index patients at HIV clinics while waiting to attend appointments. We will announce the study during the daily health information talks in the waiting rooms and interested patients can approach the recruiters. If the patient is interested and eligible, we will provide them with a study information card to give their primary partner and will set up a phone appointment to screen the partner. If both partners are interested and eligible, the couple will be invited for a secondary screening to verify that the partnership is legitimate (e.g., confirming partner names, relationship length, etc.). To ensure we capture primary partnerships, both partners will be asked, “Do you have a primary partner, meaning a person who you are committed to above anybody else and with whom you have had sexual relations?” Screenings will be interviewer-administered using tablet devices. If the couple remains eligible, both partners will provide written informed consent and be invited to participate. Partners will be consented separately to ensure a lack of coercion.

5.2 Procedures for FGDs with key stakeholders: We will conduct three FGDs with 6-8 stakeholders each. Key stakeholders will consist of HIV care providers (nurses, clinic volunteers, clinicians), community representatives and religious leaders who interact with couples who drink, and alcohol vendors (e.g., shebeen owners, local brewers). Stakeholders will be recruited using our professional networks in this region of KZN.

5.3 General procedures for the FGDs: FGDs will be conducted in private rooms at community halls or at the HSRC Sweetwaters office. [name] will train research assistants on the study objectives, interview guide, and FGD methods using a decade’s worth of training materials from studies in SSA. Research assistants will conduct the FGDs in isiZulu or English using a structured guide. FGDs will elucidate ways to make the intervention more feasible and acceptable to the target population and to obtain feedback on the curriculum. We will ask: What are your overall impressions of this program? What aspects of the program will people like/dislike the most? What types of couples and drinkers will be most/least likely to participate? How can we improve the program to increase participation among couples? If this service was offered today, would you recommend it to couples? To assess how to implement the intervention in the future, FGDs with stakeholders will elicit feedback on strategies to increase uptake of the breathalyzers by local agencies. FGDs will be audio-recorded, transcribed, and translated to English.

5.4 Training. Given the skills required to deliver MI, we will hire certified HIV testing counselors with 2+ years of counselling and/or facilitation and community experience. Facilitators and the HSRC research manager will attend a multi-day didactic training workshop (in-person, at HSRC) with [name], following a curriculum based on workshops at the Motivational Interviewing Network of Trainers and [name] prior research on couples MI. The next few weeks will consist of role-plays, practice, coaching and feedback, including mock sessions with peers and pilot couples which will be recorded for [name]. A follow-up training session will be held to cover more advanced MI skills with [name]. This will be held online

Couple-Based Motivational Interviewing with Mobile Breathalyzers to Reduce Alcohol Use in South Africa

(Zoom) several weeks after the initial training and facilitators have had time to practice. To minimize intervention drift, facilitators will be required to conduct two additional mock counseling sessions per month in English, which will be video-recorded and used in monthly booster sessions with [name] (remotely on Zoom). The project manager at HSRC will also be trained by [name] on coaching techniques to help oversee the training and role playing in Zulu and provide feedback as needed.

Before being cleared to interact with participants, facilitators will be required to demonstrate competency through three mock sessions in English.

We will also train a pair of interviewers to recruit couples and conduct assessment visits. Drs. [name] and [name] will lead additional training with staff, covering topics on couples counseling, the mobile breathalyzer technology, how to handle ethical issues with couples, health education around alcohol use and HIV, the intervention manuals and procedures, and professional conduct.

5.5 Supervision. Supervision of facilitators will occur as follows. Following each session, facilitators will listen to the audio-recording in Zulu and complete a self-assessment, identifying areas they did well, struggled with, or faced challenges with couples. The HSRC research manager or their peer facilitator will also listen to audio-recordings and complete an assessment form. Study investigators will meet with the research manager to discuss the self-assessments, and supervisor/peer assessments to assess competency and identify areas for further coaching. If budget allows, we will translate and transcribe a random set of MI sessions into English for [name] to provider further training.

[name] will provide monthly supervision to staff on intervention delivery. [name] will meet quarterly with [name] to provide strategic direction and support. PI [name] will take primary responsibility for the design, implementation and analysis of the qualitative data, working with the other co-Investigators.

5.6 Fidelity monitoring of intervention. After each session, facilitators will complete a checklist to ensure each section of the intervention was covered. Intervention sessions will be audio-recorded. The HSRC manager will listen to audio files of sessions and also complete a checklist for the sessions. Self-assessment forms described above will contain rating for key MI components (e.g., collaboration, respect, etc.). A separate space on the checklist and self-assessment forms will be provided for written comments. Completed forms will be discussed in regular Zoom calls with the team to discuss areas where further guidance is needed and to help problem-solve challenges.

5.7 Recruitment and retention. We will recruit and randomize around 120 couples to meet our target sample size of 90 couples, assuming that we will lose around 25-30% of couples after randomization. We anticipate that we will lose a very small percentage of couples due to break-ups, deaths, and migration (<5% in Uthando Lwethu), which we have accounted for in recruitment and analysis plans.

5.8 Randomization process. After informed consent and the baseline assessment, couples will be randomized to either the control arm, the couple-based MI arm, or the couple-based MI with

Couple-Based Motivational Interviewing with Mobile Breathalyzers to Reduce Alcohol Use in South Africa

mobile breathalyzers arm (MI *Plus*). We will use randomly permuted block sizes (e.g., 3, 6, and 9) generated using a computerized and secure process. The UCSF project coordinator and the HSRC data manager will use the table that the statistician created to print documents that assign participants to one of the three arms. These documents will be placed in sealed envelopes and maintained by the HSRC data manager. HSRC interviewers will take a small subset of envelopes into the field with them. At the end of the baseline survey, the index patient will be given the envelope that contains the random assignment. Couples will receive an appointment card with a date for their next study visit following randomization.

5.9 Control condition. Participants will receive the Usual Care (UC) defined by the South African national 2019 ART Clinical Guidelines (updated in March 2020). The harms of alcohol use are briefly discussed during the morning health talks in the waiting rooms of HIV clinics. HIV clients are advised that alcohol intake should be reduced to <2 standard drinkers/day for men and <1 for women for 5 out of 7 days per week. After randomization, couples in the control arm will receive brief alcohol counseling modeled off WHO guidelines and [name] intervention in Malawi, which uses participants' baseline AUDIT scores for messaging around alcohol reduction and lasts 5-10 minutes. In selecting the control, we chose to balance our ethical obligation to provide basic health information on alcohol use (minimal in this setting), while maximizing the generalizability of our findings to inform a future RCT, which will employ a UC control group. Clinical trial experts recommend the UC condition over other designs such as a time-and-attention control (TAC) when the long-term goal is to inform implementation science and scale-up. Our long-term goal will be to test the effectiveness of a scalable alcohol intervention. Moreover, because TAC designs have an active but different intervention, there is the risk of positively-biased intervention results because the comparison arm can distract participants from making reductions in alcohol use they would have otherwise made.

5.10 Procedures for mobile breathalyzers with couples in MI *Plus* arm. Drinkers will be provided with handheld breathalyzers and both partners will receive access to the breathalyzer results. Drinkers will receive SMS requests to take a breathalyzer test twice per day (e.g., in the morning at 11 am and in the evening at 8 pm). After the drinker completes each breathalyzer test, the partner receives a notification that the drinker completed a test and can view the test results. Partners will receive a unique login username and password linked to their study ID. [name] and the research manager(s) will facilitate a 1-2 hour training for couples how to use the breathalyzers/phones (e.g., charging, Wi-Fi, Bluetooth), complete breathalyzer tests, app functionality, trouble-shooting issues, and technical support. Couples will be instructed to use the breathalyzers for a 60-day period. Assessments at 60 days will allow us to assess the effects on alcohol use immediately following the 60-day intervention period.

A technology navigator will monitor daily compliance and check-in with participants to assist with login credentials, lost or damaged devices, cellular connectivity, difficulties using the phones or breathalyzers, and intentional non-use of the breathalyzers—with close monitoring during the first week. Navigators will monitor for safety issues and IPV (interpersonal violence) during routine check-ins and will provide assistance should a safety/IPV issue arise.

5.11 Survey assessments. Assessment visits will be held in community-based locations such as youth centers or in our team's mobile caravans used in other couples' studies. To minimize loss-

Couple-Based Motivational Interviewing with Mobile Breathalyzers to Reduce Alcohol Use in South Africa

to-follow-up, we will administer follow-up surveys over the phone in the case that a participant moves out of the area or is unavailable for an extended period of time. For the pilot study, surveys will be administered at baseline and 2-months (after receiving all MI sessions and/or using the breathalyzers for 60 days), and 6-months post-intervention initiation. Measures collected will be the same across visits with the exception of time-invariant variables such as demographics (collected at baseline only). All measures will be pre-tested, tailored for South Africa, and translated to *isiZulu* and back-translated to English. See Appendix with full survey instrument. Survey assessments will be interviewer-administered on tablet devices using REDCap mobile, last around 90 minutes, and uploaded to a secure web-based storage system. Partners will be assessed separately, but simultaneously, in private interview rooms.

	Domain	Measure (alphas noted are from prior studies with couples)
Primary outcomes (future trial)	Alcohol use	Number of drinking days in past 21, assessed using the three-week timeline follow-back method (TLFB) confirmed with the PEth biomarker.[32] AUDIT-C positive (score of ≥ 4 for men and ≥ 4 for women) and/or PEth positive (≥ 35 ng/ml).[33, 34]
Secondary outcomes (future trial)	Viral suppression and ART adherence	Viral suppression will be defined as less than 1000 copies/mL for DBS viral load. ART adherence will be captured using the bean method for low-literacy populations[35], by placing beans in a bowl for the number missed pills in the past 30 days. We will dichotomize adherence using a 95% cutoff, based on data showing that patients who miss $\geq 5\%$ of doses have worse virologic outcomes.[36]
	Couple communication	Constructive, avoidant, and demand-withdraw communication (communication patterns questionnaire; $\alpha=0.69-0.72$).[37]
	IPV	Physical, sexual, and emotional violence (WHO domestic violence measure; validated among PLWH; $\alpha=0.75-0.83$).[38, 39]
	Relationship dynamics	Trust (dyadic trust scale; $\alpha=0.82$).[40] Intimacy (emotional intimacy subscale of Sternberg love scale; $\alpha=0.90$).[41] Unity (inclusion of self-in-other measure).[42] Relationship satisfaction (couple satisfaction index, single item).[43] Sexual satisfaction (couple sexual satisfaction scale; $\alpha=0.89$).[44]
Mediating variables (future trial)	Shared illness appraisal	Single item that asks: "When you think about problems related to your [or your partner's] alcohol use, to what extent do you view this as "our problem" [shared by you and your partner equally] or mainly your [your partner's] own problem?".[45]
	Communal coping	Dyadic coping inventory, modified for alcohol use.[46, 47] Partners are asked how often they, as a couple, engage in activities to deal with alcohol (e.g., "We try to cope with alcohol issues together and search for solutions").
	Alcohol social support	Alcohol-specific partner support (to be adapted from the Social Provision Scale).[48]
Covariates (future trial)	Socio-demographics	Gender, age, marital status, relationship length, religion, living children, education level, household asset index.[49]

5.12 Medical record extraction. For participants living with HIV, we will access their medical record information including recent HIV results. We will obtain this information from electronic HIV registries (e.g., Tier.Net) or online databases (e.g., National Health Laboratory System), or

Couple-Based Motivational Interviewing with Mobile Breathalyzers to Reduce Alcohol Use in South Africa

by requesting clinical files from patients' HIV clinic. Participants will be asked to bring their clinic cards to study visits, which contain identifiers that can be used to look up HIV test results.

5.13 Blood samples. At screening, we will obtain consent to confirm HIV status for all participants who report being positive using a point-of-care test. We will have results in 10-15 minutes. We will base eligibility on the result of this test. We will only test potential participants who report living with HIV. We will not return test results. ***At the two-month follow-up visit, we will collect blood samples via finger pricks for testing using DBS cards. Participants who are heavy drinkers will be tested for PEth. Participants who are heavy drinkers and living with HIV will have their viral load tested.*** PEth is 95% sensitive and 73% specific for detecting heavy drinking in the past 21 days and is highly correlated with number of drinking days among PLWH in SSA. PEth samples will be processed at the United States Drug Testing Laboratories using liquid chromatography tandem mass spectrometry. PEth samples on DBS cards will be stored at the HSRC research center until they can be batch transported to the US laboratory. PEth results will be reported as positive/negative and in ng/ml. Viral load DBS samples will be processed at the Universal Pathology Laboratory (UPL) in South Africa or an HPTN Network Laboratory certified laboratory facility. Viral load DBS samples will be processed using the Aptima HIV-1 Quant Dx Assay (DBS supplement) with a lower limit of detection of 30 copies/ml. In line with standard clinical practice in South Africa, less than 1000 copies/ml will be the threshold for viral suppression.

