9.3 Study Records

9.4 Use of Information and Publications

10. References

Couple-Based Motivational Interviewing with Mobile Breathalyzers to Reduce Alcohol Use in South Africa

Study Investigators

[name]

Principal Investigator

Center for AIDS Prevention Studies

University of California, San Francisco

[name], PhD

Site Principal Investigator

Human and Social Development Programme

Human Sciences Research Council

[name]

Co-Investigator

Department of Psychology

Hunter College, City University of New York

[name]

Co-Investigator

Center for AIDS Prevention Studies

University of California, San Francisco

[name]

Co-Investigator

Center for AIDS Prevention Studies

University of California, San Francisco

Couple-Based Motivational Interviewing with Mobile Breathalyzers to Reduce Alcohol Use in South Africa

SCHEMA

Design: Formative qualitative phase followed by pilot randomized controlled trial

Population: Heterosexual couples with at least one heavy alcohol drinker on antiretroviral therapy

Study size: 40 key stakeholders and 90 couples/180 individuals (220 people total)

Study duration: 36 months

Aim 1: To develop a couple-based Motivational Interviewing intervention with mobile breathalyzer technology to deliver real-time feedback on blood alcohol content (BAC) levels. We will target heavy alcohol users with HIV and enroll their primary partner.

Aim 2: To develop and pilot test the study procedures for a future randomized controlled trial (RCT) of the couple-based intervention. We will develop and pilot test: a) training procedures; b) randomization procedures; c) the pilot study procedures; and d) data collection instruments.

Aim 3: To determine the feasibility and acceptability (F&A) of couple-based MI as a standalone intervention and when combined with mobile breathalyzers with couples to provide real-time feedback and support.

Study Site: Vulindlela/Sweetwaters community, KwaZulu-Natal, South Africa

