Our team's research in KZN suggests that a technology-based intervention will be feasible. In South Africa, smartphone penetration rates are high (82%) and of all provinces, KZN has the second highest number of 4G/LTE subscribers.[24] Mobile phones have been successfully incorporated into interventions in South Africa and elsewhere in the region.[25-27] Multiple studies at the proposed site have demonstrated the feasibility of digital interventions in HIV care. Site PI [name] demonstrated the feasibility of using an mHealth system to improve linkage-to-care after home-based testing[28] and a conversational agent (chatbot) to provide counselling for HIV self-testing.[29] These studies rely on high smartphone penetration rates and a strong mobile network. Pilot data from 2016 with PLWH in KZN (n=101) found that 96% of participants reported using a cell phone.[28] The research area is serviced by a strong network of mobile phone towers and in speed tests conducted at 14 sites spanning a distance of 60 km, we achieved an average download speed of 22.6 Mbps (3.5– 54.5 Mbps) and upload speed of 6.2 Mbps (0.05–14.2 Mbps). Although network conditions vary, speed tests show that we will have ample bandwidth to use the mobile breathalyzer technology for this study.

2.2. Aim 1

In the first phase (months 1-12), we will adapt our team's interventions to address alcohol use in South African couples living with HIV and incorporate the mobile breathalyzers.

2.3. Aim 2

As part of the first phase, we will develop the intervention manual, training procedures, randomization procedures, implementation procedures, and data collection instruments for the pilot RCT.

2.4 Aim 3

In the second phase (months 13-36), we will recruit 90 couples who will be randomized to a control arm, couple-based MI arm, and couple-based MI plus mobile breathalyzers arm. Couples will be assessed at baseline, , 2, and 6-months post intervention initiation and a subsample of 15

Couple-Based Motivational Interviewing with Mobile Breathalyzers to Reduce Alcohol Use in South Africa

couples will complete exit interviews. In months 31-36, we will analyze the F&A data, discuss the findings as a team, and identify modifications to the intervention in preparation for a future trial.

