2.5 Study design

For Aim 1, we will adapt a couple-based MI framework and interventions developed by co-I [name] (*We Test* and the *Couples Health Project*) to address alcohol use in heavy alcohol users and their primary partners and incorporate the mobile breathalyzer component. We will follow the ADAPT-ITT framework by conducting focus group discussions (FGDs) with around 40 key stakeholders to gain feedback on the intervention and then refining the intervention. For Aim 2, we will develop training procedures, study procedures, and data collection instruments that will be pilot tested during the RCT. For Aim 3, we will conduct a three-arm RCT with 30 couples randomized to the following arms (90 couples total): 1) an enhanced usual care control condition; 2) couple-based MI; and 3) couple-based MI with mobile breathalyzers for real-time feedback. For arm 2 and 3, couples will receive 3 MI sessions over a 60-day period with an experienced counselor to help strengthen communication and problem-solving skills around alcohol use. For Arm 3, couples will use the mobile breathalyzers and app for 60 days and receive the same MI sessions, which will also incorporate feedback on BAC levels (prior 30 days) and teach couples how to effectively engage with the breathalyzers. This design will allow us to assess the effectiveness of couple-based MI alone and the added synergistic effect of the mobile breathalyzers on alcohol use and HIV outcomes (e.g., adherence to antiretroviral therapy (ART), viral suppression). Our F&A outcomes will include enrollment and retention rates, satisfaction with both intervention arms, MI session attendance rates, and follow-up survey completion rates. We will also conduct qualitative interviews with a subset of 15 couples to contextualize F&A data and refine the intervention and procedures for a future full-scale efficacy trial.

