Aims 2 and 3: We will recruit couples using a combination of community-based and clinic-based recruitment approaches. Index patients who are heavy drinkers on ART for at least 6 months will be targeted first, followed by their primary partner. We will recruit around 120 couples to achieve the desired sample size of 90 couples (180 individuals). This assumes we will lose around 25-30% after randomization based on other studies at this site.

We will use a combination of active and passive recruitment strategies to enroll the sample.

Community-based recruitment: Index patients will be identified through community-based organizations or through locations in the community where drinkers can be found. Recruiters will use procedures established at HSRC to identify and recruit participants using a community mobilization approach. Individuals and couples will be targeted by a team of recruiters, who will approach potential participants in public areas in the community, such as alcohol venues (e.g., shebeens, bottle shops), markets, sports grounds, taxi ranks, HIV clinics, and community events. Recruiters will target couples together if possible, although our other studies have shown that couples are not often together in public. Potential participants will also be recruited passively (i.e., through fliers in the community). These fliers describe the study and invite interested individuals to contact the project staff by calling or sending a free “call me” SMS to the telephone number listed. Recruiters will return these messages as soon as possible and no later than the next working day.

Clinic-based recruitment: We will also actively recruit index patients at HIV clinics during morning health talks when patients are attending appointments. Recruiters will screen index patients in the waiting rooms immediately following the talks or distribute fliers/information cards so interested patients can later contact the study team if interested. We will also passively recruit index patients using fliers placed at the clinics. Clinic-based outreach teams and care providers will also help to identify HIV patients who are heavy alcohol drinkers and on ART for at least six months and refer patients to the HSRC recruiters.

Recruitment from other studies: There are other studies at the HSRC site that may be able to refer participants to the study team, for example, if they were ineligible for another study but may be interested in participating in research.

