Engagement with mobile breathalyzer technology	Proportion of breathalyzer tests taken after prompted; number of partner SMS messages sent and received on BAC results; number of drinker SMS reminders to take breathalyzer tests sent and received; average length of time to take breathalyzer tests after prompted; average number of app logins per week to access BAC data (for both partners); average user session length; number of lost/stolen phones and breathalyzers	70% completion rate	3
Retention	Retention rates; reasons for dropouts	85% retention at 2-month follow-up	All
Process outcomes	Length of MI sessions in minutes	≤90 minutes per session[9]	2, 3
Intervention fidelity	Expert ratings of quality of intervention using audio-recorded intervention sessions (checklists)	>80% inter-rater reliability	2, 3
Assessment procedures	Length of surveys; proportion of couples who complete baseline, 1, 2, and 6-month surveys	90 minutes; 75% of all couples will complete all assessments	All

Couple-Based Motivational Interviewing with Mobile Breathalyzers to Reduce Alcohol Use in South Africa

Acceptability	Proportion of couples satisfied with the intervention. Couples will decide their satisfaction together since this is a dyadic intervention.	75% of couples reporting being satisfied or very satisfied	All
---------------	---	--	-----

Couple-Based Motivational Interviewing with Mobile Breathalyzers to Reduce Alcohol Use in South Africa

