7.3 Hypotheses and methods for preliminary/exploratory analyses. Although the purpose of this study is to determine F&A rather than to conduct formal hypothesis tests, we will evaluate exploratory hypotheses as part this assessment process. For example, we expect that: H1) participants in the couples MI-only group (arm 2) will report a greater reduction in the number of drinking days (confirmed with PEth) than participants in the control group (arm 1); H2) participants in the couples MI with mobile breathalyzers group (arm 3) will report a greater reduction in the number of drinking days than participants in the couples MI-only group (arm 2). Secondarily, we also anticipate that intervention participants will report a higher odds of adherence to ART and viral suppression than those in the control arm. We also anticipate the intervention participants will report higher (indicating more positive) scores on communication and relationship dynamics and less intimate partner violence than those in the control arm. Reflecting the exploratory nature of these analyses, alpha will be set at .05 for all inferential analyses.

7.4 Power analyses. Formal tests of health outcomes or attempts to obtain valid estimates of effect sizes are not statistically justified for the proposed study. Pilot studies, by design, cannot definitively test hypotheses due to their smaller sample sizes and the frequent design adjustments necessary to maximize recruitment, retention and quality assessment of outcomes. Effect size estimates are not sufficiently reliable given the breadth of the confidence intervals. However, to supply additional information, we conducted several power analyses using NCSS PASS. In sum, our study is powered to detect small to medium distances to confidence limits for descriptive statistics and medium to large longitudinal analysis effects, though, as noted above, formal hypothesis testing will not be the focus of this F&A study.

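### The number of couples randomised is given as about 120 and as 90; Table 4 also scores an unscheduled 1-month survey and names no base for 85% retention

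*Combined protocol and SAP*

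**What the plan says.** **Number randomised.** Section 5.7 states: "We will recruit and randomize around 120 couples to meet our target sample size of 90 couples, assuming that we will lose around 25-30" per cent of couples after randomization. Section 3.2 gives the same figures: "We will recruit around 120 couples to achieve the desired sample size of 90 couples (180 individuals"), followed by "This assumes we will lose around 25-30% after randomization based on other studies at this site". Section 2.4 states that "we will recruit 90 couples who will be randomized to a control arm" and two intervention arms. Section 2.5 describes a "three-arm RCT with 30 couples randomized to the following arms (90 couples total"). The Schema gives the study size as "40 key stakeholders and 90 couples/180 individuals (220 people total"). Section 7.4 says "our study is powered to detect small to medium distances to confidence limits for descriptive statistics" and gives no number of couples.

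**Surveys.** One row of Table 4 (Section 7.2) measures the "proportion of couples who complete baseline, 1, 2, and 6-month surveys", with a threshold of 75% of all couples. Sections 3.3 and 5.11 schedule surveys at baseline, 2 months and 6 months only.

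**Retention.** Table 4 sets 85% at the 2-month follow-up, for all arms, and does not say 85% of whom. Section 3.3 lets couples who separate before the intervention leave the study. Sections 3.3 and 5.7 expect under 5% loss from separation, death and migration.

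**The concern.** The number randomised is a basic design fact. The allocation list and sealed envelopes of Section 5.8 must be prepared for one number. It also fixes the arm sizes, the participant total, and how many couples each Table 4 percentage represents.

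Table 4 matters because Section 7.2 makes the comparison of each statistic with its threshold the primary analysis, and treats a shortfall as a sign that procedures or design need remedy before a full-scale trial. A row that counts a survey nobody is scheduled to take fails automatically if scored as written. A retention row without a stated base can be scored in more than one way, and the choice could be made after the data are seen.

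**Working it through.** **Inputs.** 120 couples, 90 couples and 25-30% loss after randomization (Sections 3.2 and 5.7); 90 couples at 30 per arm (Sections 2.4 and 2.5); 40 stakeholders and 220 people (Schema); 85% retention and 75% completion (Table 4).

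**Step 1. Reproduce the plan's figure.** Number to randomise = number remaining / (1 - loss).

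- At 25% loss: 90 / 0.75 = 120, an exact match.
- At 30% loss: 90 / 0.70 = 128.6, so 129. Put the other way, 120 x 0.70 = 84 remain, which is short of 90.

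So 120 follows from 90 couples remaining and the lower end of the stated loss.

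**Step 2. What each number implies (equal allocation).**

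| Quantity | 120 randomised | 90 randomised |
|---|---|---|
| Couples per arm | 120/3 = 40 | 90/3 = 30 |
| Trial participants | 2 x 120 = 240 | 2 x 90 = 180 |
| People with 40 stakeholders | 280 | 220 |
| Couples remaining | 84 to 90 | 63 to 67.5, only if the same 25-30% loss is assumed |
| 85% retention needs | 102 | 76.5, so 77 |
| 75% completion needs | 90 | 67.5, so 68 |

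**Step 3. Try to reconcile the sections.**

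- *90 means couples remaining.* This fits 3.2 and 5.7. It does not fit 2.4 and 2.5, which say that 90 are randomised, and it leaves the Schema's 220 people 60 short of 280.
- *120 are recruited and 90 randomised.* This fits 2.5 and the Schema. It does not fit 5.7, which randomises 120, or the statements in 3.2 and 5.7 that the loss comes after randomization.

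Neither reading fits every section, and Section 7.4 gives no number that would decide between them.

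**Step 4. Completion row.** Table 4 requires four surveys (baseline, 1, 2 and 6 months). Sections 3.3 and 5.11 provide three. A couple who attends every scheduled visit has completed three of four, so the literal completion rate is 0% against a 75% threshold.

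**Step 5. Retention row.** A loss of 25-30% means 70-75% retained, which is 10 to 15 points below 85%. With 120 randomised, 84 to 90 couples are expected against 102 needed, *if* the whole loss has occurred by 2 months. On that assumption, with couples independent, the exact binomial chance of reaching 102 is about 0.6% at 75% true retention and 0.01% at 70%.

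The base can also decide the result. Suppose, as an illustration, that the whole 25% loss comes before the first session, so that 90 couples start. Over starters the threshold is 0.85 x 90 = 76.5, so 77. Any count from 77 to 90 then passes over starters and fails over the 120 randomised.

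**The case against.** The best defence is that Sections 3.2 and 5.7 explain how the two numbers relate: about 120 go in so that a target of 90 is reached. On this view 2.4 and 2.5 are loosely worded summaries, and the Schema gives a study size without saying that 90 are randomised. This stands in part. The inflation is correct, and a reader who infers a miscalculated sample size would be wrong. But it does not remove the conflict, because 2.4 and 2.5 both say in terms that 90 are randomised.

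The practical effect is also limited. Most Table 4 thresholds are percentages, and the 95% half-width around 85% changes only from 1.96 x sqrt(0.85 x 0.15/90) = 7.4 points to 6.4 points with 120. Section 7.4 disclaims formal testing. That is accepted: the case rests on a contradictory design figure, not on lost precision or power.

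The 1-month survey may be an editing remnant. The visit list in Section 2.4 has an empty place after baseline, although that could come from text conversion. Staff could sensibly score the scheduled visits only, but a prespecified criterion should not need reinterpreting.

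On retention, the loss could fall partly after 2 months. Retaining 85% at 2 months and 75% through 6 months would agree with a 25% loss (102, then 90, of 120). The protocol may mean this, but it does not say so.

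**Conclusion.** The point holds as an inconsistency. The number randomised is either about 120 or 90, a difference of 30 couples, 60 people and 10 couples per arm, and the documents do not settle which. The completion row of Table 4 cannot be met as written. These two items need correction. The retention row is a lesser point: its base is unstated, and the planned loss has not been reconciled with the 85% threshold.

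Three stronger readings are tempting and are not supported:

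- *That only 63 to 68 couples will remain.* This applies the 25-30% loss to 90 randomised couples. The documents apply it only to 120.
- *That the trial expects to fail its retention threshold.* This follows only if the loss falls by 2 months and is counted over randomised couples. The timing is not given, and the under 5% expected from separation, death and migration covers only part of the loss.
- *That the trial is too small or must enrol more.* Section 7.4 gives no number to test, and nothing here bears on whether 90 or 120 is adequate.

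The figures for 120 and 90 assume equal allocation, which Section 2.5 implies. Table 4 rows that do not depend on these points, such as session length and fidelity, are unaffected.

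**What to change.** 1. State one number randomised in the Schema and in Sections 2.4, 2.5, 3.2 and 5.7, with matching arm sizes and totals.
   - If 120: 40 couples per arm, 240 participants, 280 people, about 84 to 90 couples remaining.
   - If 90: 30 couples per arm, 180 participants, 220 people, and a stated number expected to remain (63 to 68 if the same loss is assumed).
   - If 120 are recruited and 90 randomised: 3.2 and 5.7 must place the loss before randomization.
2. Delete the 1-month survey from the completion row of Table 4.
3. Define retention over all randomised couples, with couples who start the intervention as a supplementary figure. State when the 25-30% loss is expected and reconcile it with the 85% threshold.

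The cost is mainly wording. It restates the planned figure and does not ask for more couples. If 120 is intended, the sponsor should confirm that ethics approval and budget cover 280 people and not 220; neither is in the documents, so whether they already do is unknown. Counting retention over all randomised couples may give a less favourable figure than counting starters.
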